For instance, suppose we stop after 60 patients. If the difference between the two groups' success tallies is exactly equal to 4 (the minimum given the design), the likelihood ratio (LR) in favor of having selected the truly better treatment as opposed to having made a mistaken selection equals the odds ratio (OR) raised to the 4th power. Thus, at the design alternative $p_1=0.35$, $p_2=0.20$, the LR would be 21.5. This is usually considered "very strong" evidence. Likelihood ratios in excess of 8 or 10 are generally considered to be moderate to strong evidence [Royall R. Statistical Evidence: A likelihood paradigm. 1997 Chapman and Hall/CRC]. For comparison, the usual "significant at $p < 0.05$ " corresponds to a LR of only 6.8 in large samples. Furthermore, if the design alternative holds, it is highly probable the difference between success tallies will be greater than 4. For example, if the tallies are 11 (about 30×0.35) and 6 ($=30 \times 0.20$), the LR under the design alternative is much larger (46), very strong evidence in favor of a correct selection.

To address the weight of evidence in favor of the maximum likelihood estimate (*mle*) being the true parameters as opposed to the *null* hypothesis $p_1=p_2$ being the true parameters, the generalized LR is 11.2 for the case $T=60$, $X_1=20$, $X_2=10$, which would again be moderate to strong evidence. On the other hand, if $X_1=14$, $X_2=10$, $LR=1.55$, very weak evidence against the null hypothesis. Assuming the trial does not stop at $T=60$, the above LR's will be assessed with the data at the time of selection at the observed *mle*'s for weight of evidence in favor of correct selection and for weight of evidence against the null hypothesis. The assessments will be repeated when all data have been observed, including overrun data coming in after the time of selection.

Minimizing Selection Bias

While the primary aim for the study is to select the best intervention from the 2 candidates, we are also interested in conducting point estimation and hypothesis test for the primary and secondary outcomes when appropriate and to conduct such analysis, *only* the first 30 pairs of patients can be included. This is because we will *not* enroll any additional patients if decision can be made based on the data from the first 30 pair of patients. In other words, the enrollment of 31st pair of patients and thereafter will not be necessary *unless* we don't have sufficient evidence (i.e., the difference in number of "good" outcomes is less than 4) to demonstrate one intervention is better than the other from the outcomes obtained from the first 30 pairs. Therefore, when we have to continue sampling (after the first 30 pairs) until a winner appears and use the entire sample to construct the analysis, two consequences will occur: (1) from point estimation standpoint, the probability of "good" outcome for the winner will be over-estimated (and for the loser will be under-estimated); and (2) from hypothesis testing standpoint, as sampling plan "enforces" the data to support the alternative hypothesis, bias then introduced against the null.

Nevertheless, to prevent any bias due to sampling, we propose to recruit the first 30 pairs without any look and/or comparison of their primary and secondary efficacy outcomes (unless the early stopping is required from the recommendation of DSMB due to safety concern). In such case, the recruitment of first 30 pairs of patients is independent of their outcome as we usually do for any fixed sample size design. Thus, conducting point estimation (together with a 95% confidence interval) and hypothesis testing with those 60 patients is entirely appropriate (i.e., can be done unbiasedly).

VII. References

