Study Aims and Objectives	
To assess the impact of intermediate-dose anticoagulation compared with prophylactic anticoagulation of critically ill patients with COVID-19 with regards to the composite primary endpoint of being alive and without clinically-relevant venous or arterial thrombotic events at discharge from the ICU (without transfer to palliative care unit/hospice) or at ICU duration (if ICU stay lasted 30 days or longer).
 
Clinically relevant venous or arterial thrombotic events will all be adjudicated and are defined as any of the following:
 
 • Confirmed or treated deep venous thrombosis or pulmonary embolism • Type I myocardial infarction (MI) as confirmed by a combination of biomarkers, electrocardiogram and angiogram • New ischemic stroke • Acute limb ischemia • Actionable line thrombosis requiring escalation of anticoagulation or removal or replacement of the line • CVVH Filter thrombosis requiring escalation of anticoagulation • Other thrombotic events requiring anticoagulation (e.g., intracardiac thrombosis)
Secondary Aims:	
 1. To determine the impact of intermediate-dose anticoagulation compared with prophylactic anticoagulation on the individual components of the primary outcome in the ICU. 2. To determine the impact of intermediate-dose anticoagulation compared with prophylactic anticoagulation on ICU length of stay. 3. To determine the impact of intermediate-dose anticoagulation compared with prophylactic anticoagulation on rates of acute kidney injury and renal recovery in the ICU. 4. To determine the safety of intermediate-dose anticoagulation compared with prophylactic anticoagulation with respect to major bleeding (assessed by BARC criteria, also explored by ISTH and TIMI criteria) in the ICU. 5. To determine the impact of intermediate-dose anticoagulation compared with prophylactic anticoagulation on the individual components of the primary outcome until hospital discharge 6. To determine the impact of intermediate-dose anticoagulation compared with prophylactic anticoagulation on hospital length of stay.

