Intervention /Comparator	
Intervention arm: intermediate-dose anticoagulation
 
 • If stable eGFR ≥ 30 mL/min: enoxaparin 1mg/kg SC daily or unfractionated heparin infusion at 10 units/kg/hour with goal anti-Xa 0.1-0.3 U/mL.¹ • If eGFR <30 mL/min or acute kidney injury (as defined below) or CRRT: Unfractionated heparin infusion at 10 units/kg/hour (minimum 500 units/hour if CRRT) with goal anti-Xa 0.1-0.3 U/mL.² 
Control arm: prophylaxis
 
Prophylactic dose anticoagulation (per CUIMC Guidelines):
 
 • If eGFR ≥ 30 mL/min (stable kidney function): 
 ◦ BMI < 40 kg/m2: Enoxaparin 40 mg SC daily ◦ BMI 40 – 50 kg/m2: Enoxaparin 40 mg SC q12h ◦ BMI > 50 kg/m2: Enoxaparin 60 mg SC q12h • If eGFR < 30 mL/min or acute kidney injury: 
 ◦ 50-120 kg: Unfractionated heparin 5000 units SC q8h ◦ > 120 kg: Unfractionated heparin 7500 units SC q8h 
If CRRT: Unfractionated heparin infusion pre-filter at 500 units/hour

Primary Endpoint	
Primary outcome: Composite of being alive and without clinically-relevant venous or arterial thrombotic events at discharge from ICU (without transfer to another palliative care unit/hospice) or at (if ICU duration lasted 30 days or longer).
 
Clinically relevant venous or arterial thrombotic events will all be adjudicated and are defined as any of the following:
 
 Confirmed or treated deep venous thrombosis or pulmonary embolism Type I myocardial infarction (MI) as confirmed by a combination of biomarkers, electrocardiogram and angiogram New ischemic stroke Acute limb ischemia Actionable line thrombosis requiring escalation of anticoagulation or removal or replacement of the line CVVH Filter thrombosis requiring escalation of anticoagulation Other thrombotic events requiring anticoagulation (e.g., intracardiac thrombosis)

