Secondary Endpoints	
 Composite of being alive and without clinically-relevant venous or arterial thrombotic events at discharge from the hospital (without transfer to a palliative care unit/hospice) or at 30 days (if hospital stay lasted 30 days or longer) Individual components of the primary outcome in the ICU ICU length of stay Need for renal replacement therapy Major bleeding (assessed by BARC criteria, also explored by ISTH and TIMI criteria) Individual components of the primary outcome during entire hospitalization. Hospital length of stay
Estimated Sample Size	Up to 150 subjects (to be determined by sequential randomized selection design)

[figure not shown]
¹This dose generally does not require routine monitoring of anti-Xa activity, but may be monitored by the primary team outside this study to assess for effectiveness and dose adjusted in consultation with pharmacist

²To be monitored at least 8 hours after the initiation of the infusion or any dose change.

Patients with improving kidney function or new AKI can be switched from one agent to the other within the same intervention group

Acute kidney injury defined as:

- Increase in SCr by ≥ 0.4 mg/dL within 48 hours; or
- Increase in SCr to ≥ 1.5 times baseline, which is known or presumed to have occurred within the prior 7 days; or
- Urine volume <40 mL/h for 6 hours

I. Study Population

Patient Inclusion Criteria	
 • Age >18 years of age • Confirmed diagnosis of COVID-19 by RT-PCR • New admission to eligible CUIMC ICUs within 5 days 
 ○ Transfer from nonparticipating to participating ICU is eligible if otherwise meets eligibility criteria. ○ Patients not on therapeutic anticoagulation and who were already admitted to participating ICU within 5 days of trial initiation are additionally eligible.

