Patient Exclusion Criteria	
 • Weight under 50kg • Contraindication to anticoagulation in the opinion of the treating clinician including 
 ○ overt bleeding ○ platelet count <50,000 ○ BARC major bleeding in the past 30 days ○ GI bleeding within 3 months ○ history of intracranial hemorrhage ○ Ischemic stroke within the past 2 weeks ○ craniotomy/major neurosurgery within the past 30 days ○ cardiothoracic surgery within the past 30 days ○ intra-abdominal surgery within 30 days prior to enrollment ○ Head or spinal trauma in the last months ○ History of uncorrected cerebral aneurysm or arteriovenous malformation AVM

	
 ○ Intracranial malignancy ○ Presence of an epidural or spinal catheter ○ Recent major surgery within the last 14 days ○ Decrease in hemoglobin >3 g/dL over the last 24 hours ○ Allergic reaction to anticoagulants (e.g. Heparin Induced Thrombocytopenia) as documented in the electronic health records. Extracorporeal membrane oxygenation (ECMO) support or other mechanical circulatory support. ● Severe chronic liver dysfunction (history of portosystemic HTN, esophageal varices, or Child-Pugh class C or above or similar MELD scores), abnormality in liver function tests (AST, ALT, bilirubin) 5 times greater than upper normal limit. ● History of cirrhosis ● A history of congenital bleeding diatheses or anatomical anomaly that predisposes to hemorrhage (e.g. hemophilia, hereditary hemorrhagic telangiectasia) ● Treating physician preference for therapeutic anticoagulation ● Enrollment in other concurrent trials related to anticoagulant or antiplatelet therapy ● Existing treatment with therapeutic anticoagulation during the previous 7 days of hospitalization prior to ICU admission (e.g. for VTE, atrial fibrillation, mechanical valve, etc). ● CMO orders prior to enrollment.
--	--

II. Study Procedures

- a. Screening procedures
- b. Randomization
- c. Study intervention
- d. Study Assessments and Activities

Screening procedures	All patients in participating CUIMC ICUs will be screened by the study team. Study eligibility criteria (described above) will be implemented to identify the modified intention-to-treat cohort.

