Study intervention	
 Each cluster will be randomized to one of the two antithrombotic regimens: prophylactic-dose or intermediate dose as described above. The choice of agents will be dependent upon the renal function (at the time of enrollment and every subsequent day). At the onset of study enrollment, clusters including patients admitted within the past 5 days will be randomized. Patients who meet eligibility by screening team will be enrolled. Patient is considered enrolled after a co-investigator has confirmed all inclusion/exclusion criteria have been met. Assessment of appropriateness of anticoagulation dose will occur daily based on the renal function, progressive thrombocytopenia or anemia, or development of another indication for anticoagulation such as new-onset atrial fibrillation, Patients' treatment course will be followed from randomization to hospital discharge or 30 days, whichever happens earlier. Patients will continue with randomization therapy until discharged from the ICU, except in the setting of an adverse event attributed to anticoagulation, developing an event requiring therapeutic anticoagulation, or change in code status to comfort measures. Patients transferred between participating ICUs will remain in the treatment arm assigned at initial randomization. Recommendation will be to continue study treatment if patient transferred to ICUs not participating in the present trial. If the study treatment is changed by the primary treating team in the second ICU, then patient will be evaluated by intention to treat principle. 
Intervention arm: intermediate-dose anticoagulation
 
 If stable eGFR ≥ 30 mL/min: enoxaparin 1mg/kg SC daily¹ If eGFR <30 mL/min or acute kidney injury (as defined below) or CRRT: Unfractionated heparin infusion at 10 units/kg/hour (minimum 500 units/hour if CRRT) with goal anti-Xa 0.1-0.3 U/mL² 
Control arm: Prophylactic dose anticoagulation (per CUIMC Guidelines):
 
 If eGFR ≥ 30 mL/min (stable kidney function): 
 BMI < 40 kg/m²: Enoxaparin 40 mg SC daily BMI 40 – 50 kg/m²: Enoxaparin 40 mg SC q12h BMI > 50 kg/m²: Enoxaparin 60 mg SC q12h If eGFR < 30 mL/min or acute kidney injury: • If eGFR < 30 mL/min or acute kidney injury:

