	
 ○ 50-120 kg: Unfractionated heparin 5000 units SC q8h ○ > 120 kg: Unfractionated heparin 7500 units SC q8h • If CRRT: Unfractionated heparin infusion pre-filter at 500 units/hour
Study assessment and activities	
All anticoagulation medications are standard of care according to discussions between clinician leadership in multiple disciplines and review of treatment protocols from institutions in the region and internationally. Anticoagulants will be ordered through the hospital pharmacy.
 
Patient receiving any anticoagulation are at risk for development of hemorrhage, thrombocytopenia, and in rare cases (overall rate of 0.2%) heparin induced thrombocytopenia (7). Patients who have a bleeding event may have cessation of the administered drug per clinical standard of care, and in some cases may require transfusion of blood products, and additional testing and therapy to identify and treat the source of bleeding. Patients who develop a thrombotic event may have intensification of anticoagulation per clinical standard of care.
 
We will collect all clinical, laboratory and imaging data generated per standard of care throughout the patient's hospitalization. Primary and Secondary endpoints will be assessed at ICU discharge, hospital discharge and 30 days if the patient is still hospitalized.

III. Endpoint Definition

a) Endpoint Reporting Requirements

Safety surveillance and reporting starts as soon as the patient is enrolled in the clinical investigation and will continue until the subject is deceased, the subject concludes participation in the clinical investigation or the subject withdraws from the clinical investigation.
Endpoint data will be collected throughout the time period defined above and will be entered on a CRF.

For the purposes of this investigation the following are reportable endpoints:

Death	
Deep venous thrombosis	Diagnosed on duplex ultrasonography including upper (internal jugular, subclavian, axillary/brachial) and lower extremity (iliac, femoral/popliteal, gastrocnemius, peroneal, posterior tibial) thrombosis
Pulmonary embolism	Diagnosed on CT angiography, V/Q scan, or invasive pulmonary angiography

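### For event-free patients leaving the ICU alive, the primary endpoint recognises end-of-life care only by destination, so comfort-measures patients moved to an ordinary ward count as successes

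*Combined protocol and SAP*

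**What the plan says.** Study Aims and Objectives reads the primary endpoint at "discharge from the ICU (without transfer to palliative care unit/hospice) or at ICU duration (if ICU stay lasted 30 days or longer". Its only end-of-life condition is "without transfer to palliative care unit/hospice". The Primary Endpoint section repeats the condition: "at discharge from ICU (without transfer to another palliative care unit/hospice". The wording of the fallback for long ICU stays is incomplete in both places. I take it to mean day 30, by analogy with secondary endpoint 1.

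Comfort care appears in two other places:

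- Under Study intervention, randomized therapy continues to ICU discharge except for an adverse event attributed to anticoagulation, "developing an event requiring therapeutic anticoagulation, or change in code status to comfort measures".
- The exclusion criteria list "CMO orders prior to enrollment", which does not reach later changes.

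Secondary endpoint 1 is the same composite read at "discharge from the hospital (without transfer to a palliative care unit/hospice) or at 30 days (if hospital stay lasted 30 days or longer". Study assessment and activities gives the timing: "Primary and Secondary endpoints will be assessed at ICU discharge, hospital discharge and 30 days if the patient is still hospitalized". Event Adjudication refers to definitions of thrombotic and bleeding events and has no rule for comfort care or discharge destination.

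Under Success tallies, the good or poor outcome entering the running tally is the composite primary outcome. The stopping rule needs a lead of 4, applied from 60 patients, with truncation at 100.

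**The concern.** The palliative unit/hospice condition suggests that the authors did not want a patient leaving the ICU to die to count as a success. Destination captures that intent only in part. Take two event-free patients with the same comfort-measures orders, both leaving the ICU alive. The one going to a palliative unit is a failure and the one going to an ordinary ward is a success. A third, still in the ICU under the same orders at the 30-day fallback, is also a success.

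This matters because the primary composite alone drives selection, possibly on 30 patients per arm. Secondary endpoint 1 would count a ward death by day 30 as a failure, but it does not enter the stopping rule. None of the sensitivity analyses listed for the first 60 patients concerns comfort-care status.

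**Working it through.** **Inputs.** Design success rates are 0.35 and 0.20, with a target of at least 90% correct selection (Study Implementation). A lead of 4 is needed, with a minimum of 30 per arm and a maximum of 50 per arm (Stopping and Decision rule). The rate of comfort-care transfer to a ward is not in the documents, so every rate below is an assumption.

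**Method.** I calculated the difference in tallies exactly: two independent binomials at 30 per arm, stop if the absolute difference is 4 or more, then continue pair by pair to 50 pairs. The larger tally is selected and ties are split equally.

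**Plan's own figures.** Odds ratio = (0.35/0.65)/(0.20/0.80) = 2.15. For Table 1, scenario 1, I get:

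- correct selection 95.2% (stated 95.1%)
- expected number of patients 68.4 (stated 68.4)
- truncation 10.4% (stated 10.2%)
- decision at 60 patients 62.6% (stated 62.6%)

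The design reproduces.

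**Equal mis-scoring, as a share c of failures in each arm.** Observed rate = p + (1 − p)c. Expected false successes in 60 patients = 30 × 0.65c + 30 × 0.80c = 43.5c.

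| c | observed rates | false successes in 60 | odds ratio | correct selection |
|---|---|---|---|---|
| 0 | 0.350 / 0.200 | 0 | 2.15 | 95.2% |
| 2% | 0.363 / 0.216 | 0.9 | 2.07 | 94.5% |
| 5% | 0.383 / 0.240 | 2.2 | 1.96 | 93.5% |
| 10% | 0.415 / 0.280 | 4.4 | 1.82 | 91.8% |

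**Equal mis-scoring, as a share m of all patients in each arm.** Rates are 0.35 + m and 0.20 + m. For m = 2%, 5%, 10% and 15%, correct selection is 94.8%, 94.3%, 93.6% and 93.1%.

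**Worst case: mis-scoring in the worse arm only.** Rates are 0.35 and 0.20 + m.

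| m | odds ratio | correct selection |
|---|---|---|
| 2% | 1.91 | 92.2% |
| 3.3% (1 in 30) | 1.77 | 89.7% |
| 5% | 1.62 | 85.8% |
| 10% | 1.26 | 69.9% |

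The 1-in-30 row is a rate that persists for as long as enrolment continues, not a single fixed patient.

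**The case against.** **The effect is small if balanced.** This stands. Correct selection stays above 90% in every balanced row shown. Only a difference between arms breaks the target, and nothing in the documents shows one. It cannot be excluded either: treatment follows room cluster, and blinding is stated only for the adjudicating physicians, not for the staff who set code status and destination.

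**The model leans upward.** This also stands. It applies c to all failures, but a patient who dies in the ICU or has a thrombotic event fails anyway and cannot become a false success by this route. The plan also does not say whether 0.35 and 0.20 already count comfort-care ward transfers as successes.

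**The later horizon is covered.** This stands in part. An ICU-discharge reading matches the treatment period and is a defensible choice. Secondary endpoint 1 and the hospital-wide components pick up ward deaths, and secondary outcomes can help break a tie at truncation. None of this changes the tally. The three assessment times under Study assessment and activities add no criterion to the primary endpoint.

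**Stronger readings.** Two are tempting, and the documents support neither:

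- A reader might infer from the room-type changes under Randomization procedures that scoring depends on bed availability. That text concerns negative-pressure and other rooms in participating ICUs and says nothing of ward, palliative or hospice beds.
- A reader might infer that dying patients fail only by destination. That holds only for event-free patients who leave the ICU alive; death in the ICU or a thrombotic event is a failure wherever the patient would have gone.

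**Conclusion.** The gap is real on the literal text of both statements of the primary endpoint, and no other section closes it. It is an inconsistency in scoring that feeds the selection rule, and it is worth correcting because correction is cheap. It does not show that the selection procedure fails. Under the assumed balanced rates of 2% to 10% of failures, the loss is 0.7 to 3.4 percentage points (95.2% to 94.5–91.8%), probably an overstatement. Falling below 90% needs mis-scoring concentrated in the worse arm at about 1 patient in 30, which is a worst case and not a prediction. Both the frequency and any difference between arms are unknown from the documents.

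**What to change.** In Study Aims and Objectives and in Primary Endpoint, keep the palliative unit/hospice condition and add that a patient with comfort-measures-only orders in force at ICU discharge, or at day 30 if still in the ICU, is a poor outcome. Complete the fallback wording at the same time. In secondary endpoint 1, apply the same rule at hospital discharge or day 30.

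Settle this before outcomes are compared by arm, and confirm that the CRF captures code status and its date. The plan collects all clinical data generated during the hospitalization, so the information should be obtainable, but no dedicated field is named. If the sponsor keeps the present definition, the minimum is a pre-specified re-run of the selection tally under the status rule as a sensitivity analysis.

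The change affects scoring only, not care. It costs a sentence in each place and slightly lower success rates, and a rare comfort-care patient who survives would be scored as a failure. Code status remains a clinical decision, so the rule removes the dependence on destination but not every influence of unblinded staff. Ward deaths of patients without comfort orders at ICU discharge would still be covered only by the hospital/30-day secondary endpoint.

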To avoid bias in statistical inference due to bias in sampling, *only* the first 60 patients will be included in this set of analysis. Details explain why bias occurs and how it will affect the statistical inference can also be found in the supplemental appendix. We will use the data from these 60 patients to generate the proportions of patients with the events specified as primary and secondary outcomes. We will also report the descriptive statistics (mean, median, interquartile range) for the time to ICU discharge. Graphical display of the data will be done as well. To compare the intervention effect between the two study groups on the primary and secondary outcomes, we will use generalized linear model with identity link function for continuous variables and logit link function for dichotomous variables following the intent-to-treat principle. Covariates in these models include intervention group indicator, ICU indicators, and the potential confounding factors. The pre-specified potential confounders are age, sex, weight, estimated glomerular filtration rate (eGFR), concomitant treatment with an IL-6 inhibitor, and concomitant treatment with corticosteroids. Generalized estimating equations methodology will be employed to account for the within-ICU correlation for subject assignment to the same ICU area. The key parameter of interest is the regression coefficient corresponding to the intervention group indicator which is the mean difference for continuous outcomes and log-odds ratio for dichotomous outcomes and it represents intervention effect of intermediate-dose anticoagulation compared with that of prophylactic anticoagulation. To report the trial findings, we will present the mean difference and odds ratio when appropriate and their corresponding p-values and 95% confidence intervals. Several pre-specified sensitivity analyses will be conducted: (1) excluding the patients who undergo CRRT during the study period; (2) excluding patients who experienced deviation in anticoagulation from randomized treatment arm; (3) analyzing the patients as the treatment they actually received. Additional sensitivity analysis will also be conducted to include covariates found imbalanced between the two intervention groups.

Operating characteristics of the Study Design

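### The intermediate-dose regimen for stable eGFR of 30 mL/min or more is stated two ways, with conflicting anti-Xa monitoring footnotes for its heparin infusion

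*Combined protocol and SAP*

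**What the plan says.** The experimental regimen is set out twice in the combined protocol and SAP.

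- **Protocol outline, Intervention /Comparator.** For stable eGFR of 30 mL/min or more, the intermediate arm may receive "enoxaparin 1mg/kg SC daily or unfractionated heparin infusion at 10 units/kg/hour with goal anti-Xa 0.1-0.3 U/mL". The marker for footnote 1 follows the anti-Xa goal.
- **Section II, Study intervention.** For the same patients the entry reads "If stable eGFR ≥ 30 mL/min: enoxaparin 1mg/kg SC daily¹". It gives no infusion option and no anti-Xa goal.
- **Both places, eGFR below 30, acute kidney injury or CRRT.** The regimen is "Unfractionated heparin infusion at 10 units/kg/hour (minimum 500 units/hour if CRRT) with goal anti-Xa 0.1-0.3 U/mL", marked with footnote 2.

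The footnotes stand below the outline table. Footnote 1 says the dose generally needs no routine anti-Xa check, and that the primary team may check it outside the study. Footnote 2 calls for monitoring eight hours or more after the infusion starts or its dose changes. A further note adds: "Patients with improving kidney function or new AKI can be switched from one agent to the other within the same intervention group".

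The analysis plan for the first 60 patients lists three sensitivity analyses. The second is "excluding patients who experienced deviation in anticoagulation from randomized treatment arm". The third analyses patients by treatment received. Deviation has no operational definition.

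**The concern.** This is the experimental arm. Two sets of current text describe its treatment for one renal stratum, and nothing says which governs. The Study intervention section refers back to the earlier description and then restates it differently, so it does not read as a deliberate change.

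Staff working from different pages could give different agents. Staff giving the infusion could also follow different monitoring rules for an anticoagulant with a stated anti-Xa target. That bears on delivered treatment and on safety oversight. It also bears on what a reader, or a later phase 3 trial, would take intermediate dose to have meant.

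The statistical consequence is narrower. A patient with stable eGFR of 30 or more on the infusion follows the outline but is on an agent not listed for that patient under Study intervention. Whether the second sensitivity analysis excludes that patient depends on a definition the plan does not give.

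**Working it through.** The plan gives no figure on this point, so the check is a comparison of texts followed by simple bounds.

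**Step 1. The regimens side by side (intermediate arm).**

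| Renal stratum | Outline, Intervention /Comparator | Study intervention |
|---|---|---|
| Stable eGFR 30 or more | Enoxaparin, or heparin infusion with anti-Xa goal; footnote 1 | Enoxaparin only; footnote 1 |
| eGFR below 30, AKI or CRRT | Heparin infusion with anti-Xa goal; footnote 2 | Same; footnote 2 |

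The control-arm regimens also agree between the two places. The mismatch is confined to one option, in one stratum, of one arm.

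**Step 2. The footnotes.** In the outline, both strata give the infusion at 10 units/kg/hour with goal anti-Xa 0.1-0.3 U/mL. One line carries footnote 1 and the other footnote 2, so the same infusion and goal have two monitoring rules. If footnote 1 was meant for enoxaparin alone, as it is placed under Study intervention, then the infusion at stable eGFR of 30 or more has a goal but no monitoring footnote of its own. Neither reading leaves a clear rule for that line.

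**Step 3. How a patient reaches the ambiguous cell.** There are two routes:

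- The patient is started on the infusion at stable eGFR of 30 or more, as the outline allows.
- The patient starts it with AKI or low eGFR, recovers, and stays on it. The switching note is permissive for improving kidney function, while Study intervention says "The choice of agents will be dependent upon the renal function (at the time of enrollment and every subsequent day".

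A patient on the listed enoxaparin dose complies with both texts and is not exposed.

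**Step 4. Deviation status.**

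| Reading of deviation | Outline governs | Study intervention governs |
|---|---|---|
| By randomized arm | Not a deviation | Not a deviation |
| By listed agent | Not a deviation | Deviation |

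The classification changes in one cell of four.

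**Step 5. Size.** The first-60 set has 30 patients per arm. If k intermediate-arm patients are on the infusion at stable eGFR of 30 or more, an agent-level reading against Study intervention leaves 30 − k in the second sensitivity analysis, before any other exclusions. The value of k is not in the documents. As an assumption, over 0% to 50% of the arm:

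- k = 0: 30 − 0 = 30 remain
- k = 3 (10%): 30 − 3 = 27 remain
- k = 6 (20%): 30 − 6 = 24 remain
- k = 15 (50%): 30 − 15 = 15 remain

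Each patient moved is 1/30 = 3.3% of the arm.

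**Step 6. What does not move.** The selection rule uses success tallies, a lead of 4, a minimum of 60 patients and truncation at 100. The Table 1 scenarios add only the two success probabilities. The main models follow intention to treat. None of these uses the agent given, the anti-Xa goal or deviation status.

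**The case against.** The strongest reply is that the slip is editorial and nearly harmless. Its parts fare differently.

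- **Deviation is worded against the randomized arm, not the agent.** Both agents belong to the intermediate arm, and switching within the arm is foreseen. On that reading nobody is reclassified. This is a fair reading and may be the intended one, but the plan does not state it, and the switching note is tied to changes in kidney function.
- **The footnote conflict is a misplaced marker.** Under Study intervention, footnote 1 sits on enoxaparin with no goal, so nothing conflicts there. Footnote 2 speaks of an infusion, and footnote 1 is permissive. This stands as to cause and limits the conflict to the outline. It does not settle the monitoring rule for the infusion in that stratum.
- **The sentence "The choice of agents will be dependent upon the renal function" is not a further contradiction.** This stands. The outline's options also depend on renal function: two at stable eGFR of 30 or more, one below.

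A reader might also infer that the as-treated analysis changes. The documents do not support this. That analysis excludes no one, and a patient on this infusion would most naturally be classed as intermediate under either text, because both list it under that arm and the control arm has no weight-based infusion.

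**Conclusion.** The contradiction is real and in current text. For intermediate-arm patients with stable eGFR of 30 mL/min or more, the two statements of the permitted agents cannot both govern. The infusion also carries a monitoring footnote at odds with the one on the identical infusion in the next line.

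Permitted treatment and monitoring are therefore ambiguous for patients given the infusion in that stratum. Their status in the second sensitivity analysis is ambiguous only if deviation is judged by listed agent. The number affected is unknown; the range of 30 down to 15 patients retained is an assumption, not an estimate.

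Two stronger readings are tempting. One is that delivered treatment and deviation are undefined for the whole arm. The other is that every intermediate-arm patient with stable eGFR of 30 or more is affected. Neither is supported: the remaining regimens agree, and patients on the listed enoxaparin dose comply with both texts. The selection rule and the intention-to-treat analyses are untouched. No view is taken on which regimen or monitoring rule is right.

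**What to change.** 1. Reconcile the Intervention /Comparator row, the footnotes below the outline table, and the Study intervention section. State the agent options for stable eGFR of 30 mL/min or more, and the footnote that applies to each option, once; elsewhere, cross-refer to that text. Which option and monitoring rule to keep is for the sponsor to decide.
2. In the analysis plan for the first 60 patients, and in the outline's Design row that repeats it, state whether deviation in the second sensitivity analysis is judged by randomized arm or by listed agent. Settle this before deviation status is assigned and without reference to outcomes.
3. Report how many intermediate-arm patients received the infusion while at stable eGFR of 30 or more, so that readers can see the size of the issue.

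The cost is protocol and SAP wording plus one tabulation. No extra patients are needed, and the plan already collects clinical and laboratory data from standard care.
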